# Analysis of primary endpoint

Patient recruitment will be defined as the proportion of eligible patients recruited from the total number of eligible patients. This will be reported with 95% CI calculated using a binomial test for proportions.

# Analysis of secondary endpoints

## Overall disease progression

The proportion of patients whose disease has progressed will be reported, split by type of progression (MRI, serum PSA and prostate biopsy). The proportion of patients displaying no disease progression, progressing by any, and progressing by all types will also be reported. The main analysis will compare the proportion of patients that received active treatment and display disease progression to those that received placebo, stratified by the other treatment (3 levels for aspirin stratification and two for vitamin D3), presented for both aspirin (both doses combined) and vitamin D3. The proportion of patients whose disease has *regressed* will also be reported, following the same methods outlined above.

Additional analyses will compare low dose aspirin to placebo and high dose to placebo, again stratified by the other treatment (Vitamin D3). Further supplementary analyses will look at all 6 treatment groups and explore treatment interactions.

## Disease progression by logistic regression

Five logistic regression models will be run to determine the effect of treatment on disease progression. For all models aspirin (0 = placebo, 1 = 100mg, 2 = 300mg) and vitamin D3 (0 = placebo, 1 = active) will be used as predictors. The main analysis will be unadjusted for covariates but secondary analyses will be adjusted for age, BMI, serum hormone levels (testosterone, FSH, LH), and CCP score. An interaction term between aspirin and vitamin D3 will be included in some secondary analyses. Also included will be a trend test p-value for the 3 aspirin treatments.

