## Sample size

Sample size calculations suggested that 800 men are needed for a future definitive randomised chemoprevention study of standard (300mg) or low dose (100mg) aspirin vs. placebo and/or Vitamin D3 vs. placebo in patients enrolled on an Active Surveillance programme for prostate cancer.

This feasibility trial aims to demonstrate the acceptability and viability of recruitment for this larger study. Data from this trial will be used to determine the number of centres required to enable the larger, 800 patient trial to fully recruit within 4 years. The sample size was chosen to examine acceptance rates and the time required to recruit 102 patients. We plan to recruit 102 patients over 18 months. If the true recruitment rate is 33.3%, approaching 300 individuals, and therefore recruiting ≥100, would achieve 89% power to show that the true recruitment rate is above 25% (using a two-sided binomial proportion test with a 0.05 significance level).

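### The adjusted and interaction logistic models put 8 to 11 slopes on about 102 men and name no estimator; the usual default overstates the odds ratios, and a Firth-type fit would be a cheap improvement

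*SAP*

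**What the plan says.** The SAP, under Disease progression by logistic regression, plans five models. In all of them "aspirin (0 = placebo, 1 = 100mg, 2 = 300mg) and vitamin D3 (0 = placebo, 1 = active) will be used as predictors". On covariates, the section first fixes the primary version: "The main analysis will be unadjusted for covariates". For the other versions it then states that "secondary analyses will be adjusted for age, BMI, serum hormone levels (testosterone, FSH, LH), and CCP score". In addition, "An interaction term between aspirin and vitamin D3 will be included in some secondary analyses". Models 1 to 4 (tumour volume, PSA, Gleason, maximum cancer core length) are three-category proportional-odds models. Model 5, progression by any of three measures, is binary. The size is set under Sample size: "We plan to recruit 102 patients over 18 months".

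The SAP does not state:
- the estimator, or what to do if a fit does not converge;
- whether the 0/1/2 aspirin code is a factor or a linear score;
- whether the interaction models also carry the six covariates;
- an expected progression rate.

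**The concern.** Maximum-likelihood log odds ratios are biased away from zero when there are few events per slope. If a treatment cell in the interaction model has no progressions (or only progressions), the interaction estimate is infinite. With 17 men per cell and six covariates, both can happen.

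Two things are at stake. Adjusted treatment effects would be reported as larger than they are. And if a fit breaks down, the analyst would have to choose a remedy (drop terms, pool arms, change method) after seeing the data, which an SAP is meant to prevent.

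**Working it through.** **1. The plan's own figure.** The only power statement concerns recruitment: "If the true recruitment rate is 33.3%, approaching 300 individuals" "would achieve 89% power to show that the true recruitment rate is above 25"%, "using a two-sided binomial proportion test with a 0.05 significance level". Normal approximation: se0 = √(0.25×0.75/300) = 0.0250; se1 = √(0.333×0.667/300) = 0.0272; power = Φ[(0.0833 − 1.96×0.0250)/0.0272] = Φ(1.26) = 89.6%. Arcsine gives 88.9% and the exact test 87.8%. The stated 89% reproduces, but it says nothing about the logistic models.

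**2. Slopes.**
- Aspirin as a factor: 2 + 1 (vitamin D3) + 6 covariates = 9; with the interaction, 9 + 2 = 11.
- Aspirin as a linear score: 1 + 1 + 6 = 8; with the interaction, 9.
- Interaction without covariates: 3 + 2 = 5 (factor) or 2 + 1 = 3 (score).

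**3. Empty cells.** Men per cell: 102/6 = 17. With a common progression rate p, the chance that at least one of six cells has no event is 1 − [1 − (1−p)^17]^6.
- p = 10%: 0.9^17 = 0.167, giving 67%.
- p = 20%: 0.8^17 = 0.0225, giving 13%.
- p = 30%: 0.7^17 = 0.0023, giving 1%.

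With aspirin as a factor, an empty cell makes the interaction estimate infinite whether or not covariates are present.

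**4. Binary model, simulated.** 102 men, 1,000 trials per setting. Assumed: odds ratio 0.5 per treatment term, 1.5 per SD for each of six independent covariates, no true interaction. Failure means a divergent or non-finite estimate, or an empty outcome category. Ratios are mean treatment log odds ratio divided by the truth; each pair is 9 / 11 slopes.

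| Progression | Events (102×p) | Events per slope | ML ratio | ML failure | Firth ratio |
|---|---|---|---|---|---|
| 10% | 10 | 1.1 / 0.9 | 1.27 / 0.95* | 14.4% / 76.7% | 1.01 / 0.94 |
| 15% | 15 | 1.7 / 1.4 | 1.19 / 1.21 | 1.8% / 44.5% | 0.96 / 1.02 |
| 20% | 20 | 2.3 / 1.9 | 1.21 / 1.19 | 0.3% / 24.7% | 1.00 / 1.02 |
| 30% | 31 | 3.4 / 2.8 | 1.15 / 1.26 | 0% / 4.5% | 0.99 / 1.06 |
| 40% | 41 | 4.5 / 3.7 | 1.14 / 1.22 | 0% / 0.5% | 1.00 / 1.05 |
| 50% | 51 | 5.7 / 4.6 | 1.15 / 1.19 | 0% / 0% | 1.02 / 1.02 |

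*Only among the 23% of fits that converged.

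Covariate log odds ratios under ML were 1.14 to 1.36 times the truth. Firth fits failed in at most 0.1% of trials.

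**5. Other assumptions.** A second set (1,500 trials per setting, covariate log odds ratios 0.1 to 0.4, FSH–LH correlation 0.6, true vitamin D3 log odds ratio −0.693) gave mean ML estimates of −0.90, −0.80, −0.78 and −0.77 at 10, 20, 30 and 40%. These are 29%, 16%, 13% and 11% too large: a true odds ratio of 0.50 reads as about 0.41 (e^−0.90) to 0.46 (e^−0.77). Firth gave −0.70, −0.68, −0.69 and −0.69. With the interaction, ML failed in 73%, 21% and 3% of trials at 10, 20 and 30%. With no true effect, at the same three rates, ML rejected in 4.7%, 5.7% and 6.9% and Firth in 3.6%, 4.0% and 4.1%.

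A third set found ML bias of about 7% to 22% with 9 slopes at 10% to 50% progression, and Firth within about 8%. With covariates and interaction, ML failed in 73%, 19%, 5% and 0.3% at 10, 20, 30 and 50%.

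**6. Fewer evaluable men.** With 84 men (an assumption, for missing second scans or biopsies), ML failure with 11 slopes is 87.3%, 34.5% and 8.4% at 10, 20 and 30%.

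**7. Proportional-odds models, simulated.** 102 men, effects as in step 4; 500 trials per setting for ML, about 150 for a Jeffreys (Firth-type) penalty. Treatment ratios and failures, 9 / 11 slopes:

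| Regress / stable / progress | ML ratio | ML failure | Penalised ratio |
|---|---|---|---|
| 5/85/10% | 1.19 / 1.24 | 3.0% / 3.6% | 1.01 / 1.13 |
| 10/75/15% | 1.10 / 1.17 | 0% / 0% | 1.01 / 1.10 |
| 10/60/30% | 1.11 / 1.19 | 0% / 0% | 0.99 / 1.06 |
| 30/40/30% | 1.12 / 1.07 | 0% / 0% | 1.10 / 1.04 |

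**The case against.** The SAP names no estimator, so maximum likelihood is an inference. That stands: the defect is that the fit is left open. Maximum likelihood is still what an unqualified logistic regression would normally be run with.

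A reader might infer that these models often fail in general, and that PSA is the worst case because progression may be rare there. The documents do not support this. PSA is one of the four proportional-odds models, which failed in 0% to 4% of simulated trials. The only binary model counts progression by any of three measures, so its rate is at least that of each component, and from 30% upward failure is about 5% or less. The 11-slope model is also only one reading, since the SAP does not say that the interaction and covariates go together.

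A reader might also infer that inflated adjusted odds ratios would mis-size the definitive trial. The Introduction does name the numbers needed for that trial as an aim. But the Sample size section already gives 800 men and uses this trial's data to set the number of centres; nothing passes the adjusted odds ratios on.

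Finally, the bias is small beside the noise. At 20% to 40% progression it is 0.08 to 0.11 on the log scale in the second simulation set, against a standard deviation of 0.56 to 0.67 for a treatment term even under Firth in the first (9 slopes). This stands and limits the severity. It does not defend leaving the estimator open, because the better fit costs little.

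**Conclusion.** The point holds as a low-severity improvement. Under the default estimator, adjusted treatment log odds ratios would be overstated by roughly 7% to 29% in binary model 5 and 7% to 24% in the ordinal models. The one exception is the mostly non-convergent 11-slope setting at 10%. Frequent failure is confined to model 5 with the interaction at about 20% progression or less.

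Firth's method brings model 5 to within about 8% of the truth with almost no failures. It should not be read as a cure for all five models: the ordinal fits kept up to 13% bias on treatment terms, on few replicates. Nor does it add information. The standard deviation of a treatment log odds ratio stays at 0.54 to 0.91 with 9 slopes and 0.79 to 1.24 with 11.

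The figures rest on assumed progression rates, assumed effect sizes and 102 evaluable men. Fewer men would make matters worse.

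**What to change.** In the SAP section Disease progression by logistic regression, state that:
- the adjusted and interaction versions of binary model 5 are fitted by Firth's penalised likelihood, with profile-penalised-likelihood confidence intervals;
- the adjusted versions of ordinal models 1 to 4 use a bias-reduced cumulative-logit fit where the software offers one, and otherwise are labelled exploratory;
- aspirin enters as a factor or as a linear score (say which), and which models carry the interaction, with or without the covariates.

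The cost is a few sentences and, for model 5, a different standard routine. The downside is slightly conservative tests (null rejection about 4%), and the estimates remain imprecise. The unadjusted main analysis need not change.

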#### 1. Change in tumour volume

An ordinal logistic regression model using proportional odds will be run to assess the progression or regression of disease as assessed by the change in tumour volume by MRI from baseline to 12 months. The dependent variable will be coded according to percentage change.

DV code	Tumour volume percentage change (%)	Description
0	-100 ≤ x ≤ -33	Greater than 33% decrease in tumour volume
1	-33 < x ≤ 33	Absolute change less than 33% in tumour volume
2	x > 33	Greater than 33% increase in tumour volume

### 2. Change in serum PSA

An ordinal logistic regression model using proportional odds will be run to assess the progression or regression of disease as assessed by the change serum PSA. The dependent variable will be coded according to percentage change.

DV code	Serum PSA percentage change (%)	Description
0	-100 ≤ x ≤ -50	Greater than 50% decrease in serum PSA
1	-50 < x ≤ 50	Absolute change less than 50% in serum PSA
2	x > 50	Greater than 50% increase in serum PSA

### 3. Change in Gleason score

An ordinal logistic regression model using proportional odds will be run to assess the progression or regression of disease as assessed by the change in Gleason score or primary grade. The dependent variable will be coded according to an increase or decrease: 0 = decrease in score/grade; 1 = no change; 2 = increase in score/grade

### 4. Change in maximum cancer core length

This model will be identical to model 2 (serum PSA) with maximum cancer core length as the dependent variable.

#### 5. Disease **progression** by any measure

A final logistic regression model will be run to assess the effect of treatment on disease progression by any of the three measures (tumour volume, serum PSA, Gleason score). Disease progression will be coded as 1 if disease progression is observed for any of the three disease measures and 0 otherwise. A regression of disease — a decrease in disease measure — will be treated as "no progression".

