## Change in maximum cancer core length (MCCL)

Disease progression/regression will also be defined as a 50% increase/decrease in maximum cancer core length

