### Survival analysis

Five proportional hazards model will also be run to look at early drop-out, with and without the disease progression measures above (including by *any* measure). Kaplan-Meier curves will be used to illustrate time to drop-out for the different treatments.

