## Supplementary analyses

## Change in disease progression measures

The effect of treatment on the non-dichotomised change in disease measures will be explored. The differences in tumour volume, serum PSA and maximum cancer core length from baseline to 12 months will each be treated as the dependent variable. Serum PSA will be transformed to log (1+PSA). Patients without a second MRI or biopsy will be excluded from specific analyses where change was based on that measure.

Linear regression will be used to assess the effect of each treatment on disease progression, both univariate (treatment Y/N), and adjusted for the other treatment. Further analyses will adjust for serum hormone levels (testosterone, FSH, LH), and include an interaction term between aspirin and vitamin D3.

A Wilcoxon rank sum test will be performed to look at treatment differences using the change from baseline for each disease measure. For aspirin, the 100mg and 300mg doses will be combined for comparison to the placebo and also compared separately. All tests will be stratified by the other treatment and un-stratified. A Wilcoxon test for trend (Cuzick test) will also be carried out to determine whether there is an increased change in disease measure with increased aspirin dose.

Further exploratory analyses to look at time to change may be undertaken using a mixed effects model applied to log (1+PSA). As before, aspirin and vitamin D3 will be included as predictors, with an interaction effect and covariates included. Covariates may include age, BMI, or hormone levels. The interaction term will be removed if not significant. A plot of log (1 + PSA) will be generated, containing the predicted trajectories by treatment arm.

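### Model 5 (progression by any measure) has no rule for men without a 12-month assessment, and its tumour-volume component is narrower than the SAP's own MRI definition of progression

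*SAP*

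**What the plan says.** SAP, section 5 (Disease progression by any measure), builds the outcome on "any of the three measures (tumour volume, serum PSA, Gleason score" and codes it so: "Disease progression will be coded as 1 if disease progression is observed for any of the three disease measures and 0 otherwise". The next sentence assigns regression to the non-progression category. Missing assessments are not mentioned.

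Four other parts of the SAP bear on this:

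- **Overall disease progression** reports proportions "split by type of progression (MRI, serum PSA and prostate biopsy", and then: "The proportion of patients displaying no disease progression, progressing by any, and progressing by all types will also be reported".
- **Disease progression by MRI** gives three routes to progression: a volume increase of at least 33%; an upgrade to stage T3 or above; or, with no lesion at screening, a new lesion of at least 0.2cc scored PIRADS 4 or 5. Model 1 (Change in tumour volume) codes percentage volume change alone.
- **Change in maximum cancer core length (MCCL)** states: "Disease progression/regression will also be defined as a 50% increase/decrease in maximum cancer core length". Model 4 handles it separately: "This model will be identical to model 2 (serum PSA) with maximum cancer core length as the dependent variable".
- **Change in disease progression measures**, under Supplementary analyses, has the only rule on missing assessments: "Patients without a second MRI or biopsy will be excluded from specific analyses where change was based on that measure".

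The Survival analysis section and the section on hormone levels and CCP both reuse progression by any measure.

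**The concern.** Not having been seen to progress is not the same as having been assessed and found stable. The coding rule puts both kinds of men in category 0. If loss before 12 months differs between arms, the arm that loses more men looks better, with or without a treatment effect.

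Separately, the descriptive proportion and the model 5 odds ratio carry the same label, but the SAP does not ensure that they classify the same men in the same way. The MRI component may be the full definition or only the volume change of model 1. The biopsy component may be Gleason alone or Gleason with MCCL. Two programmers could follow the text and produce different datasets.

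**Working it through.** **The plan's own figure.** The SAP has no power or precision figure for progression. Its one power figure, 89%, is for recruitment: 300 approached, 33.3% against 25%, two-sided 0.05. The critical proportion is 0.25 + 1.96 × √(0.25 × 0.75/300) = 0.299. Then z = (0.333 − 0.299)/√(0.333 × 0.667/300) = 1.25, giving 89%. It reproduces and is not in dispute.

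**Inputs.** From the SAP: 102 men in 6 balanced groups, 102/6 = 17 each, so vitamin D3 is 51 vs 51 and each aspirin level has 34. Assumed: true progression of 30% in both arms, and m, the share of men with none of the three assessments at 12 months, unrelated to progression.

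**Unassessed men coded 0.** Observed risk = 0.30 × (1 − m). SE(log OR) = √[1/(n·p₁(1−p₁)) + 1/(n·p₀(1−p₀))].

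| m, placebo / active | Observed risk | OR | Shift, 51 vs 51 | Shift, 34 vs 34 |
|---|---|---|---|---|
| 10% / 10% | 0.27 / 0.27 | 1.00 | 0 | 0 |
| 10% / 20% | 0.27 / 0.24 | (0.24/0.76)/(0.27/0.73) = 0.85 | 0.158/0.455 = 0.35 SE | 0.158/0.557 = 0.28 SE |
| 10% / 30% | 0.27 / 0.21 | (0.21/0.79)/(0.27/0.73) = 0.72 | 0.330/0.467 = 0.71 SE | 0.330/0.571 = 0.58 SE |

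With the larger loss on placebo the odds ratios are the reciprocals, 1.17 and 1.39. At 40% true progression, the second and third rows give 0.84 and 0.69.

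**Does another section already settle this?** The exclusion rule sits under the supplementary change analyses and works measure by measure. It does not mention PSA. It cannot say what a composite should be when one component is missing and the others are negative. The Survival analysis section has "Kaplan-Meier curves will be used to illustrate time to drop-out for the different treatments", which would reveal unequal loss but would not change model 5.

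**MRI component.** The table takes tumour volume in model 5 to mean the model 1 coding.

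| Case | MRI definition | Model 1 | Model 5, other components negative |
|---|---|---|---|
| T3 upgrade, stable volume | progression | code 1 | 0 |
| No baseline lesion, qualifying new lesion | progression | percentage undefined | 0 |
| Volume change exactly +33% | progression | code 1, labelled as below 33% | 0 |
| Volume change exactly −33% | regression | code 0 | 0 |

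**MCCL.** A man whose only progression is in MCCL is 0 in model 5. In the descriptive analysis he is either a progressor by biopsy or not, depending on a definition that the SAP does not give.

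**The case against.** Several points on the other side stand in whole or part.

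- A reader might infer that the SAP instructs missing men to be scored as non-progressors, or that it contradicts its own exclusion rule. Neither is supported. The sentence after the coding rule is about regression, which suggests that missing data were not in mind, and the exclusion rule concerns different outcomes. The defect is a rule that gives this result when followed as written, with nothing elsewhere to prevent it.
- A reader might infer that leaving MCCL out of model 5 is a mistake. The section says three measures twice and comes directly after the MCCL model, so the omission may be deliberate. Nor is a gain from including it shown. If MCCL-only men share the full treatment effect, adding them helps precision. But start from 0.25 vs 0.167 and let MCCL add 10% of non-progressors unrelated to treatment: risks become 0.25 + 0.075 = 0.325 and 0.167 + 0.083 = 0.25, and the odds ratio weakens from 0.60 to 0.69. What stands is the unclear biopsy type in the descriptive analysis.
- Model 1 does what its title says. A volume model need not capture stage, and percentage change needs a baseline lesion. The problem is that model 5 takes over the term tumour volume.
- The +33% mismatch touches only exact ties. The PSA and MCCL definitions at 50% are not written as inclusive, so models 2 and 4 do not clearly contradict them.
- The shifts are below one standard error and rest on assumed rates.

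**Conclusion.** The point holds for model 5. As written, its zero category mixes men assessed as stable with men not assessed, and its MRI component can miss men who meet the SAP's own definition of progression. Under the assumptions shown, with loss unequal by 10 to 20 percentage points, the odds ratio under no effect is 0.85 to 0.72, or 0.28 to 0.71 standard errors. With equal loss and no effect there is no bias. How many men are affected by the MRI and biopsy ambiguities cannot be worked out from the SAP.

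A reader might infer that the trial's main result is at risk. It is not: the primary endpoint is recruitment, and nothing is powered on progression. This should be corrected because a named composite outcome is not reproducible as written and the correction is cheap.

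**What to change.** 1. In model 5, code 1 if any assessed component meets its definition; 0 only if MRI, PSA and biopsy were all assessed at 12 months and none does; missing otherwise. Add sensitivity analyses with the missing men all coded 0 (which reproduces the literal rule) and all coded 1, and one restricted to men with every component assessed.
2. Use the full MRI definition for the MRI component of model 5, and state that model 1 is limited to men with a baseline lesion.
3. Use one definition of any progression in Overall disease progression, model 5, Survival analysis and the hormone and CCP section, with MCCL in or out throughout.
4. Set the upper cut of model 1 at 33% or more, to match the MRI definition.

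**Cost.** SAP wording and recoding of planned data; no new visits or measurements. Some men leave model 5. In the 10%/20% and 10%/30% examples, 45.9 + 40.8 = 86.7 and 45.9 + 35.7 = 81.6 of 102 remain, before losing partly assessed men with no positive component.

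**Downside.** Keeping known progressors while dropping incomplete non-progressors can overstate progression. Let q be the share of men missing at least one component, unrelated to progression. In the extreme where every progressor among them still shows on an available component, the estimate is 0.30/(1 − q + 0.30q). That is 0.30/0.93 = 32% at q = 10% and 0.30/0.86 = 35% at q = 20%, against a true 30%. The analysis restricted to fully assessed men does not have this distortion under the same assumption, and the all-0 and all-1 analyses show how far the result depends on the missing men.

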## Biochemical disease progression

Biochemical disease progression (or regression) will be defined as a 50% increase (or decrease) in serum PSA at 12 months from baseline.

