## Study period and visits

The study will last for 18 months (plus ≥30 days for pharmacovigilance). Data will be collected at 3-monthly intervals. Secondary endpoint measures will be carried out at the following times:

- MRI taken at baseline and 12 months
- Prostate biopsy at baseline and 12 months for pathology review & CCP score analysis.
- Serum PSA measured at baseline and every 3 months until 18 months
- Serum testosterone, FSH, and LH at baseline and every 6 months until 18 months
- Serum vitamin D3 taken at baseline and every 6 months until 18 months
- Serum calcium at screening and 6, 12, and 18 months

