## Effect of serum hormone levels and CCP on disease progression

A logistic regression model will be run to determine whether final measurements of testosterone, FSH and LH, or final CCP score has an effect on overall disease progression (progression by *any* measure). It will be adjusted by the baseline measurements.

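### Model 5's coding rule, taken literally, counts men with missing 12-month assessments as non-progressors (minor; cured by a wording change)

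*SAP*

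**What the plan says.** The SAP section on disease progression by any measure (model 5) builds a composite from MRI tumour volume, serum PSA and Gleason score. Its rule is: "Disease progression will be coded as 1 if disease progression is observed for any of the three disease measures and 0 otherwise". The next sentence adds only that regression counts as no progression. There is no missing category.

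All three components depend on the 12-month visit. Study period and visits lists "MRI taken at baseline and 12 months" and "Prostate biopsy at baseline and 12 months". PSA is drawn every 3 months, but biochemical progression "will be defined as a 50% increase (or decrease) in serum PSA at 12 months from baseline".

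The one rule on absent assessments is under Supplementary analyses, in the section on change in disease progression measures: "Patients without a second MRI or biopsy will be excluded from specific analyses where change was based on that measure".

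The any-measure outcome is used again. The drop-out models in Survival analysis are run "with and without the disease progression measures above", and the any-measure version is named there. The section on hormone levels and CCP uses it as the dependent variable. Separately, Overall disease progression states: "The proportion of patients displaying no disease progression, progressing by any, and progressing by all types will also be reported". That section gives neither a coding rule nor a denominator.

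**The concern.** A man becomes a 1 only if progression is seen, and every other man becomes a 0. Two kinds of men then receive a 0 that their data do not support:

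- men with nothing assessed at 12 months;
- men with one or two components assessed, none showing progression, and the rest missing.

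The SAP expects such men. It plans analyses of early drop-out, and elsewhere it excludes men who lack a second MRI or biopsy. That exclusion covers analyses of change in a single measure and gives no rule for a three-part composite. If it were stretched to model 5, it would discard men whose PSA progression was observed but whose biopsy was missed, against the any-measure definition.

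At stake are the any-progression rate, which is biased downwards, and the treatment odds ratio (OR) from model 5.

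**Working it through.** **The plan's own figures.** The SAP gives no progression rate, drop-out rate or effect size for this outcome, so there is nothing on this point to reproduce. Its one power figure (89% for the recruitment rate, 300 approached, 33.3% v 25%) does reproduce: 89.6% by normal approximation, 88.9% by arcsine, 87.8% exact. It has no bearing here.

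**Inputs.** From the SAP: 102 men; three equal aspirin levels, so 68 men on either aspirin dose v 34 on placebo. Assumed: 12-month progression risks of 15% by MRI, 20% by biopsy and 10% by PSA, independent, and the missing fractions shown.

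**Formula.** True composite = 1 − 0.85 × 0.80 × 0.90 = 0.388. If a fraction d of men have missing data and a share q of those men still show progression on what was assessed, the coded rate = (1 − d) × 0.388 + d × q. With nothing assessed, q = 0. With only the biopsy missed, q = 1 − 0.85 × 0.90 = 0.235. With only the MRI missed, q = 1 − 0.80 × 0.90 = 0.280.

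**Effect on the rate, d = 20%**

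| Missing | Coded rate |
|---|---|
| Nothing assessed | 0.8 × 0.388 = 31.0% |
| Biopsy only | 0.310 + 0.2 × 0.235 = 35.7% |
| MRI only | 0.310 + 0.2 × 0.280 = 36.6% |

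The largest shift is 7.8 points. The 95% half-width at 102 men is 1.96 × √(0.388 × 0.612 / 102) = 9.5 points.

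**Effect on the OR, no true effect.** With equal missingness the OR stays at 1. With unequal missingness (placebo v active):

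| Missing | 10% v 25% | 10% v 15% |
|---|---|---|
| Nothing assessed | 0.349 v 0.291, OR 0.77 | OR 0.92 |
| Biopsy only | 0.373 v 0.350, OR 0.91 | OR 0.97 |
| MRI only | 0.377 v 0.361, OR 0.93 | OR 0.98 |

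If placebo men miss more, the OR moves above 1. For the largest shift, at 68 v 34 men, the SE of the log OR is √[1/(68 × 0.291 × 0.709) + 1/(34 × 0.349 × 0.651)] = 0.448. The 95% interval around 0.77 is then about 0.32 to 1.84.

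**Effect on the OR, true effect.** Take 25% v 40%, OR 0.50, with nothing assessed in 20% of each arm: 0.25 × 0.8 = 0.20 and 0.40 × 0.8 = 0.32, so OR = (0.20/0.80)/(0.32/0.68) = 0.53. At 10% and 30% missing it is 0.52 and 0.55. If only one component is missed, the direction varies. With an effect on biopsy alone (11.1% v 20%, composite OR 0.74) and 20% missing in both arms, missing biopsies give 0.78 and missing MRIs give 0.73.

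**Check of alternative rules.**

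- *Keep partly assessed men only if they progressed.* With the biopsy missed in 10%: (0.9 × 0.388 + 0.1 × 0.235)/(0.9 + 0.1 × 0.235) = 40.4%. With 25% missed, 43.2%. Both exceed the true 38.8%, and 10% v 25% gives an OR of 1.13 when the truth is 1.
- *Men with all three components only.* This is unbiased if the biopsy is missed at random (simulated OR 1.005 against a truth of 1). If the biopsy is missed by 40% of PSA progressors and 10% of others, the rate is (0.06 + 0.81 × 0.32)/0.87 = 36.7%. The current coding gives 0.10 + 0.9 × (0.9 × 0.32 + 0.1 × 0.15) = 37.3%.
- *Multiple imputation of missing components.* In that same PSA-dependent case, simulation gives 38.8%, the true value.

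**The case against.** The best defence is that the literal reading was not meant. Models 1 to 4 use three levels, model 5 collapses them to two, and the sentence after the rule explains that regression falls into the 0 group. On that view, 0 covers regression or no change among men who were assessed. This is plausible, and no miscoding has been shown to have happened. But the restriction to assessed men is not written, and supplying it still leaves partly assessed men unsettled. Two programmers could build different datasets from this sentence.

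The objection to size stands. Every rate above is assumed, the OR of 0.77 needs a wide imbalance in men with nothing assessed, and even that shift lies well inside its own interval.

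A reader might infer three stronger points. The SAP does not support them.

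- *That the proportions in Overall disease progression carry the same error.* That section has no zero-by-default rule. Its types are MRI, PSA and biopsy; MRI progression as defined elsewhere includes stage upgrading and new lesions, and biopsy could include core length. It need not be the model 5 variable.
- *That the planning of the definitive trial is undermined.* The SAP says this trial's data will set the number of centres for an 800-man study. It does not say that the any-progression rate will be an input.
- *That every reuse is equally affected.* Men without a 12-month biopsy have no final CCP score, so they would leave the CCP model anyway. The hormone model can still be affected.

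**Conclusion.** The coding sentence for model 5 is wrong as written, at minor severity. Applied literally, it lowers the any-progression rate whenever a missed assessment would have shown progression not seen on another component. It moves the OR away from 1 under no effect if missingness differs by arm, and slightly towards 1 under a true effect when equal shares of men have nothing assessed. The sizes depend on the assumed component risks, their independence and the assumed missing fractions. All of the shifts shown are smaller than sampling error at about 102 men. This is a secondary model in a feasibility trial, and the recruitment endpoint does not depend on it. The point is worth correcting because the rate error has only one direction and the cure is cheap.

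**What to change.** In the model 5 section:

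1. Code 1 when any component shows progression. Code 0 only when all three components were assessed at 12 months and none shows progression.
2. Set men with no component assessed to missing.
3. For partly assessed men, make multiple imputation of the missing components the main handling, and analysis of men with all three components the sensitivity analysis. The order matters, since the complete-component set can do worse than the present coding (36.7% v 37.3%, true 38.8%).
4. State that partly assessed men are neither set to 0 by default nor kept only if they progressed.

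Use the same variable in the drop-out models and in the hormone and CCP models. If the any-progression proportion in Overall disease progression is taken from this variable, report it on the same evaluable denominator.

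The cost is a few lines of SAP text and one extra analysis run. With about 17 men in each of six cells (102/6), the imputation model must be kept small. The complete-component set has a smaller N and drops some men with observed progression. No option removes bias if missingness depends on the unobserved outcome: with a true rate of 45%, and 30% of progressors and 10% of non-progressors lost, the assessed-only rate is 0.315/(0.315 + 0.495) = 38.9%. The present coding would give 31.5%.
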